8.4 Reporting Procedures

8.4.1 Serious Adverse Event Reporting

When an Investigator determines that an AE meets the protocol definition of an SAE during the study, he/she must notify the Sponsor using an SAE Report Form **within 24 hours of the study site personnel's knowledge of the event**, regardless of the Investigator assessment of the relationship of the event to study drug. Relevant information will be entered on the AE page and on all other applicable pages of the CRF; source documentation should not be sent with the SAE Report Form unless requested.

Follow-up information received on SAEs should be emailed or faxed to the Sponsor within 1 business day of receipt (refer to [Medical Monitor / Sponsor Information Page](#) for contact information). This information should be included on a follow-up SAE form and filed with the original SAE information.

All SAEs will be followed until resolution, until the condition stabilizes, until the event is otherwise explained, or until the subject is lost to follow-up.

The completed SAE Report Form should be submitted via email or fax to the SAE Reporting Contact which can be found on the [Medical Monitor / Sponsor Information Page](#) of this protocol.

Do not delay reporting a suspected SAE in order to obtain additional information. Any additional information, if collected, can be reported as a follow-up to the initial report.

8.4.2 Regulatory Reporting Requirements for Serious Adverse Events

Prompt notification by the Investigator to the Sponsor of SAEs (even for non-interventional post-marketing studies) is essential so that legal obligations and ethical responsibilities towards the safety of subjects and the safety of a product under clinical investigation are met.

The Sponsor has a legal responsibility to notify both the local regulatory authority and other regulatory agencies about the safety of a product under clinical investigation. The Sponsor will comply with country-specific regulatory requirements relating to safety reporting to the regulatory authority, IRB/IEC, and investigators.

Investigator safety reports are prepared for suspected unexpected serious adverse reactions according to local regulatory requirements and are forwarded to Investigators as necessary.

An Investigator who receives an investigator safety report describing a SAE(s) or other specific safety information (e.g., summary or listing of SAEs) from the Sponsor will file it with the Investigator's Brochure and will notify the IRB/IEC, if appropriate, according to local requirements.

8.5 Pregnancy Management and Reporting

Any female subject who becomes pregnant during the study will be withdrawn. Details will be collected for all pregnancies in female subjects and female partners of male subjects that begin after the start of dosing and through the Follow-up visit. Pregnancy is not automatically considered an AE.

If a pregnancy is reported, then the Investigator should complete a Pregnancy Report Form and submit via email or fax to the Pregnancy Reporting Contact for which contact information can be found on the [Medical Monitor / Sponsor Information Page](#) of this protocol, within 2 weeks of learning of the pregnancy. The subject will also be followed to determine the outcome of the pregnancy. Information on the status of the mother and child will be forwarded to the Sponsor. Generally, follow-up will be no longer than 6 to 8 weeks following the estimated delivery date. Any premature termination of the pregnancy will be reported.

Any SAE occurring in association with a pregnancy brought to the Investigator's attention after the subject has completed the study and considered by the Investigator as possibly related to the study drug must be promptly reported to the Sponsor or the Sponsor's representative.

The Investigator must attempt to collect pregnancy information on any female partners of male study subjects who become pregnant while the subject is enrolled in the study. Pregnancy information must be reported to the Sponsor or the Sponsor's representative as described above. The partner will also be followed to determine the outcome of the pregnancy. Information on the status of the mother and child will be forwarded to Sponsor or the Sponsor's representative. Generally, follow-up will be no longer than 6 to 8 weeks following the estimated delivery date. Any premature termination of the pregnancy will be reported on the Pregnancy Report Form.

9 Data Management

For this study, subject data will be entered into the Sponsor-defined CRFs, transmitted electronically to the Sponsor or designee, and combined with data provided from other sources in a validated data system.

Management of clinical data will be performed in accordance with applicable Sponsor standards and data cleaning procedures will be used to ensure the integrity of the data, e.g. errors will be corrected, and inconsistencies queried in the data.

Adverse events and relevant medical history will be coded using the most current version of the Medical Dictionary for Regulatory Activities. Concomitant medications will be coded with the most current version of World Health Organization Drug Global Dictionary.

The Investigator will retain original source documents and the Sponsor will receive CRF-required data as electronic datasets. Subject initials will not be collected or transmitted to the Sponsor.

10 Statistical Considerations and Data Analyses

This study is intended to show that tapinarof cream has a favorable safety and efficacy profile during repeated, intermittent treatment courses over an extended period of time.

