s. Subjects will be monitored for disease worsening (vIGA-ADTM ≥2), and study drug may be started at any time during the observation period. If an unscheduled visit is required for re-start of study drug, then the vIGA-ADTM must be completed.

t. For subjects receiving study drug, subjects or their caregivers will be instructed to apply study drug QD at the approximate same time each day, based on subject or caregiver preference.

u. For subjects receiving study drug, study drug will be applied after safety assessments have been conducted, [REDACTED]

v. Subjects who withdraw from the study before Visit 13 (Week 48) will complete an ET visit. A follow-up visit is not required for a subject who early terminates.

w. Phone calls to assess AEs and concomitant medications, to review study drug application procedures (if applicable), and to confirm subject's continued participation in the study. Subjects should be reminded to complete the diary and bring it with them to the next clinic visit.

AD = atopic dermatitis; AE = adverse event (s); BMI = body mass index; %BSA = percent body surface area; C = collect; [REDACTED]; CRF = case report form; CV = cardiovascular; D = dispense; [REDACTED]; ET = early termination; EASI = Eczema Area and Severity Index; FU = follow-up; [REDACTED]; NA = not applicable; P/C = phone call; PK = pharmacokinetic;

[REDACTED]; PP-NRS = Peak Pruritus-Numeric Rating Scale; QD = once daily; WOCBP = women of child-bearing potential; V = visit; vIGA-ADTM = Validated Investigator Global Assessment in Atopic Dermatitis.

1 Introduction

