4.2 Inclusion Criteria

Each subject must meet all of the following criteria to be eligible to participate in the study:

For Rollover Subjects Only:

1. Met the criteria as a Study Completer in one of three parent studies (Phase 3 pivotal safety and efficacy study DMVT-505-3101, Phase 3 pivotal safety and efficacy study DMVT-505-3102, or Phase 2 maximal use PK study DMVT-505-2104) and was still receiving study drug at the last visit of one of these studies.

NOTE: To meet the criteria as a Study Completer in one of the three parent studies, a subject must have completed $\geq 80\%$ of the intended doses in that study.

2. Female subjects of childbearing potential must have a negative urine pregnancy test at Baseline (Day 1).

For Direct-Enrolling Subjects Only:

3. Male and female subjects ages 2 years to < 18 years at the time of consent with clinical diagnosis of AD by Hanifin and Rajka criteria [[Hanifin, 1980](#)] (see [Appendix 1](#)).
4. Subjects with a vIGA-AD™ score of ≥ 3 and AD covering $\geq 40\%$ of the BSA at Screening and Baseline (pre-randomization), or subjects with a vIGA-AD™ score of 2 at Screening and Baseline (pre-randomization) regardless of BSA. Scalp should be excluded from the BSA calculation to determine eligibility during Screening and at Baseline, and for all efficacy assessments. Subjects must have screened for the DMVT-505-3101 or DMVT-505-3102 study and failed to meet BSA and/or vIGA-AD™ eligibility criteria.

NOTE: Subjects with disease only on palms and soles are not eligible.

5. AD present for at least 6 months for ages 6 years old and above or 3 months for ages 2 to 5 years old, confirmed by prior medical documentation and/or according to the subject/caregiver report.
6. Female subjects of childbearing potential must have a negative serum pregnancy test at Screening and a negative urine pregnancy test at Baseline (Day 1).

For All Subjects (Rollover Subjects and Direct-Enrolling Subjects):

7. Female subjects of childbearing potential who are engaging in sexual activity that could lead to pregnancy should use one of the following acceptable birth control methods while on study and for 4 weeks after the last exposure to study drug.

- Acceptable contraception methods include intrauterine device, hormonal contraceptives, barrier method (e.g., condom or diaphragm), or surgical sterilization of male partner (vasectomy)

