- Subjects who claim abstinence as their method of contraception are allowed provided they agree to use a barrier method (e.g., condom or diaphragm) should they become sexually active from Baseline to 4 weeks after the last dose of study drug

Non-child-bearing potential is defined as:

- premenarchal
- pre-menopausal females with a documented bilateral tubal ligation, bilateral oophorectomy, hysterectomy, or hysteroscopic sterilization
- postmenopausal female with a cessation of menses for at least 12 months without an alternative medical cause; a blood sample with follicle stimulating hormone > 40 mIU/mL is confirmatory in questionable cases

8. Subject, subject's parent(s), or legal representative must be capable of giving written informed consent/assent, which includes compliance with the requirements and restrictions listed in the consent/assent form; written informed consent must be obtained prior to any study related procedures.

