7.5 Follow-Up Visit 14; Week 49 (Day 344 ±3 Days)

Subjects will return to the study site 1 week (± 3 days) after last treatment to complete follow-up assessments as follows:

- Brief physical examination
- Vital signs measurement
- Blood sample collection for clinical laboratory tests (serum chemistry and hematology)
- Urinalysis
- vIGA-AD™ score (excluding subject's scalp)
- %BSA affected calculation (excluding subject's scalp)
- EASI (excluding subject's scalp)
- [REDACTED]
- [REDACTED]
- PP-NRS (by subject or caregiver)
- [REDACTED]
- [REDACTED]

- AE recording
- Concomitant medication recording

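### Pregnancy collection in Protocol 8.5 stops at the Follow-up visit, about 1 week after last treatment, although contraception is required for 4 weeks; for early terminators the end point is undefined

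*Protocol*

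**What the plan says.** - **Collection window.** The first paragraph of Protocol 8.5 covers pregnancies in female subjects and in female partners of male subjects "that begin after the start of dosing and through the Follow-up visit".
- **Timing of that visit.** Section 7.5 schedules it 1 week (± 3 days) "after last treatment to complete follow-up assessments as follows". Section 7.8 also places it one week after the end of treatment. The visit table in SAP Section 7 has Week 48 at Day 337 and Week 49 at Day 344.
- **Early terminators.** Table 1, footnote v: "A follow-up visit is not required for a subject who early terminates".
- **Contraception.** Criterion 7 in Section 4.2 applies to female subjects of childbearing potential whose sexual activity could lead to pregnancy. It requires an acceptable method "while on study and for 4 weeks after the last exposure to study drug". Subjects relying on abstinence must agree to a barrier method "should they become sexually active from Baseline to 4 weeks after the last dose of study drug".
- **Other reporting text in 8.5.** The second paragraph has no date limit: "If a pregnancy is reported, then the Investigator should complete a Pregnancy Report Form". For the period after study completion, a pregnancy-associated SAE "considered by the Investigator as possibly related to the study drug must be promptly reported to the Sponsor". The partner paragraph refers to partners "who become pregnant while the subject is enrolled in the study".
- **Testing.** Table 1 marks the urine pregnancy test at Visits 2 to 13 and at Early Termination (ET), and leaves Week 49 blank.

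**The concern.** The protocol asks women to avoid pregnancy for 4 weeks after last exposure, but its stated rule for collecting pregnancies closes after about the first of those weeks. A site that follows the first paragraph of 8.5 exactly has no duty to collect a pregnancy that begins in the remaining weeks. For a woman who terminates early, the visit that closes the window need not take place, and no other visit or date is named.

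The study runs for 48 weeks, has safety as its first objective, and includes adolescent and adult females. Data on pregnancies that begin soon after exposure could therefore be incomplete. What is at stake is the completeness of safety data. Endpoints, sample size and analyses are not affected.

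**Working it through.** **Inputs**

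| Quantity | Value | Source |
|---|---|---|
| Contraception after last exposure | 4 weeks | Protocol 4.2, criterion 7 |
| Last treatment to Follow-up | 1 week ± 3 days | Protocol 7.5 |
| Week 48 visit | Day 337 ± 3 | SAP Section 7 |
| Week 49 Follow-up | Day 344 ± 3 | SAP Section 7 |
| Follow-up for early terminators | not required | Protocol Table 1, footnote v |

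**The plan's own interval.** 344 − 337 = 7 days, which agrees with the stated 1 week.

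**Woman treated to Week 48.** Contraception period = 4 × 7 = 28 days. Days outside the collection window = 28 − (days from last treatment to Follow-up):

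- nominal: 28 − 7 = 21 days
- with the ± 3 days of Section 7.5 (visit 4 to 10 days after last treatment): 28 − 10 = 18 to 28 − 4 = 24 days
- if the Week 48 and Week 49 visits each move by 3 days independently, the interval is 341 − 340 = 1 to 347 − 334 = 13 days, and the gap is 15 to 27 days

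**Completers who stopped earlier.** Treatment stops whenever vIGA-AD reaches 0. With Follow-up on Day 344 there is no gap if the last dose was on or before Day 344 − 28 = Day 316. A subject who stopped at Week 44 (Day 309) and was not re-treated has Follow-up 344 − 309 = 35 days later, past the 28 days.

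**Early terminators.** Section 8.5 states no end point, so any figure rests on an assumption:

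- *A: collection stops at the ET visit, d days after last dose.* Gap = max(0, 28 − d). For d = 0, 7, 14 and 28 this gives 28, 21, 14 and 0 days.
- *B: collection runs to the scheduled Day 344, last dose on Day L.* Gap = max(0, L + 28 − 344) = max(0, L − 316). For L = 316 it is 0 days; for L = 320 it is 4 days.

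**Whether other text closes the gap**

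1. The Pregnancy Report Form sentence is undated but follows a dated one. It can be read as covering any later report or as limited by the paragraph before it. On either reading it acts only once someone reports.
2. The post-study clause in 8.5 and the post-discharge clause in 8.1 cover only SAEs judged possibly or reasonably related. Section 8.1.2 counts a congenital anomaly as an SAE. Section 8.5 says pregnancy is not automatically an AE, so an uncomplicated later pregnancy triggers neither clause.
3. Section 8.1 does not oblige investigators to seek AEs or SAEs in former subjects.
4. No pregnancy test is scheduled after Week 48 or ET, so capture depends mainly on what the subject or caregiver reports.

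**The case against.** The strongest reply is that no rule is broken. Criterion 7 is a precaution placed on the subject, Section 8.5 is a data-collection duty placed on the site, and nothing in either document says the two periods must match. Section 8.5 also goes some way towards handling late reports. The form sentence has no date limit, its two-week clock runs from when the investigator learns of the pregnancy, and the pregnancy must be followed to outcome. Because the window depends on when a pregnancy begins, one that began before the Follow-up visit but was recognised afterwards is already included. For early terminators, a site would probably treat ET as the closing visit, since Section 7.7 includes a pregnancy test and AE recording there. Finally, the consent forms and part of the protocol's risk section are not available; they may explain the 4 weeks or already ask for self-report.

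Much of this stands and keeps the point small. There is no inconsistency in the strict sense, the form sentence may well be read broadly, and the unseen text limits the point to the wording of 8.5. It does not remove the gap. The undated sentence needs a volunteered report and a favourable reading, and the post-study clauses need a related or possibly related SAE. Treating ET as the end point gives early terminators a definite end, but for a woman seen on the day of her last dose it leaves all 28 days uncovered. Neither assumption A nor B is stated in 8.5.

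**Conclusion.** The concern holds, as a minor point about safety-data collection. For a female subject treated to Week 48, about 21 of the 28 required contraception days (18 to 24 under Section 7.5) lie outside the stated pregnancy-collection window. There is no gap when the last dose was 28 or more days before Follow-up. For early terminators the end point is undefined, and the gap ranges from 0 to 28 days depending on the assumption made and the date of last dose.

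The number of women affected cannot be estimated from the documents. The visible text gives no reason for choosing 4 weeks, and no known fetal risk in that period is claimed here.

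**What to change.** Amend Section 8.5 as follows:

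- For female subjects, collect details of every pregnancy that begins after dosing starts and up to the later of (a) the Follow-up visit, or the ET visit for those who terminate early, and (b) 4 weeks after the last dose of study drug. Say explicitly that early terminators are included.
- At the last visit, ask subjects or caregivers to tell the site about any pregnancy that began in that period, including one recognised later.
- State that the Pregnancy Report Form requirement applies to such reports.

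The rule for female partners of male subjects can stay as it is, because criterion 7 does not apply to them.

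The cost is a wording change and a request at a visit already scheduled, with no added visit or test. A few more pregnancies may have to be followed to outcome, and capture in the added weeks will still rely on self-report. No endpoint or analysis changes.

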10.1 General Considerations

All study data will be summarized using descriptive statistics for the ITT population overall and by the following categories: received tapinarof treatment in either DMVT-505-3101 or DMVT-505-3102; received vehicle treatment in either DMVT-505-3101 or DMVT-505-3102; received tapinarof treatment in DMVT-505-2104; and enrolled directly into DMVT-505-3103. Categorical variables will be reported using frequency and percentage (e.g., sex, race). Continuous variables will be reported using number of subjects, mean, standard deviation (SD), median, minimum, and maximum. All efficacy and safety data will be listed by subject.

10.2 Determination of Sample Size

The sample size of this study is based on the ICH E1A guideline on extent of population exposure to assess clinical safety for drugs intended for long-term treatment of non-life-threatening conditions. Up to 961 subjects will be enrolled in this study across all regions, including up to 836 rollover subjects from studies DMVT-505-3101, DMVT-505-3102, and DMVT-505-2104 and approximately 125 subjects directly enrolling into this study.

10.3 Analysis Populations

All subjects enrolled into the study will be included in the ITT population.

10.4 Planned Analyses

All efficacy and safety measures over the course of the study will be presented. All analyses will be based on the ITT population. Details of planned analyses will be described in the Statistical Analysis Plan, which will be finalized prior to database lock.

10.4.1 Disposition and Demographics

Demographic and baseline characteristics as well as medical history will be summarized using the ITT population, including frequency and percentages for categorical variables and mean, SD, median, minimum, and maximum for continuous variables.

The numbers of subjects will be summarized by the following categories: received tapinarof treatment in either DMVT-505-3101 or DMVT-505-3102; received vehicle treatment in either DMVT-505-3101 or DMVT-505-3102; received tapinarof treatment in DMVT-505-2104; and enrolled directly into DMVT-505-3103.

10.4.2 Efficacy Analyses

All efficacy analyses will be performed based on the ITT population as described above. Summaries will be presented overall and by the following categories: received tapinarof treatment in either DMVT-505-3101 or DMVT-505-3102; received vehicle treatment in either DMVT-505-3101 or DMVT-505-3102; received tapinarof treatment in DMVT-505-2104; and enrolled directly into DMVT-505-3103. Summaries of efficacy endpoints by visit will be performed using OC and LOCF methods.

Efficacy endpoints are as follows:

For subjects entering the study with a vIGA-AD™ score of clear (0):

- [REDACTED]
- Proportion of subjects who never experience vIGA-AD™ ≥ 2 throughout the study
- [REDACTED]

[REDACTED]

[REDACTED]

[REDACTED]

[REDACTED]

For subjects entering the study with a vIGA-AD™ score ≥ 2 :

- Proportion of subjects who achieve vIGA-AD™ = 0 or 1 at least 1 time during the study
- [REDACTED]

The following endpoints will be summarized over subjects in the ITT population:

- [REDACTED]
- [REDACTED]
- [REDACTED]
- [REDACTED] change and percent change from Baseline in %BSA affected by visit (OC and LOCF)
- [REDACTED]
- [REDACTED] change and percent change from Baseline in EASI score by visit (OC and LOCF)
- Proportion of subjects with $\geq 50\%$ improvement in EASI score from Baseline by visit (OC and LOCF)
- Proportion of subjects with $\geq 75\%$ improvement in EASI score from Baseline by visit (OC and LOCF)
- Proportion of subjects with $\geq 90\%$ improvement in EASI score from Baseline by visit (OC and LOCF)
- Mean change in PP- NRS score from Baseline at each study visit
- Proportion of subjects with a Baseline PP-NRS score ≥ 4 who achieve ≥ 4 -point reduction in the PP-NRS from Baseline at each study visit

• [REDACTED]
[REDACTED]

For analyses of time to event, such as the time to first worsening (vIGA-ADTM ≥ 2) or the time to first reaching a vIGA-ADTM score of 0, the Kaplan-Meier product limit method will be used to estimate the median time (if estimable). If the median is not estimable (e.g., < 50% of subjects reach the event), other methods for estimating the median and/or other percentiles will be applied.

The remaining efficacy endpoints will be summarized descriptively as follows: continuous data will include the mean, SD, minimum, maximum, median, and number of observations; descriptive summary statistics for categorical data will include frequency counts and percentages.

10.4.3 Safety Analyses

The ITT Population will be used in the analysis of safety data. Summaries will be presented overall and by the following categories: received tapinarof treatment in either DMVT-505-3101 or DMVT-505-3102; received vehicle treatment in either DMVT-505-3101 or DMVT-505-3102; received tapinarof treatment in DMVT-505-2104; and enrolled directly into DMVT-505-3103.

The number and percent of subjects with TEAEs will be summarized by system organ class, and preferred term for all TEAEs, all TEAEs considered by the Investigator to be related to study drug, all SAEs, all TEAEs leading to study drug discontinuation, and all TEAEs leading to study discontinuation. TEAEs will be defined as follows:

- For rollover subjects, all AEs reported in DMVT-505-3103 will be considered to be a TEAE except for those AEs ongoing at the end of the parent study (DMVT-505-3101, DMVT-505-3102, or DMVT-505-2104) but resolved prior to the Visit 1 date in DMVT-505-3103.
- For subjects enrolled directly into DMVT-505-3103, all AEs that start after the first dose of study medication will be considered to be a TEAE.

Data listings will be provided for subjects who discontinued the study due to an AE and for subjects with an SAE.

Laboratory values will be classified as normal, low or high based on normal ranges supplied by the laboratory. Changes from Baseline in abnormality status will be summarized using shift tables. For quantitative laboratory measures, observed values and changes from Baseline will be summarized descriptively by visit.

Observed vital sign values (systolic and diastolic blood pressure, pulse rate, and body temperature) and change from Baseline in vital signs will be summarized similarly to the laboratory values.

LTS scores will be summarized by visit for subject (or caregiver) overall assessment and Investigator overall assessment separately.

• [REDACTED]
[REDACTED]
[REDACTED]
[REDACTED]
[REDACTED]
[REDACTED]
10.4.5 [REDACTED]
[REDACTED].

